### **3.2.4 Date of last administration of BRV**

Date of last administration of BRV will be defined as last administration of BRV while in the study as recorded in the Study Termination (Dropout) or (Completed Subject) CRF pages. If the date is partial, then use the imputation of partial end dates rules as described in [Section 4.2.2](#).

For the snapshot analyses described in [Section 4.3](#), patients ongoing in the study will not yet have a date of last administration of BRV recorded. For these patients the date of last administration of BRV will be imputed using the date of the data cut off so that an estimate of the exposure to date can be calculated.

For patients who have completed or withdrawn from the study, if the date of last administration is missing, then the last end date from the BRV Medication CRF page (applying the imputation of partial end dates rules as required) will be used. If that date is also missing then the date of first BRV administration as described in [Section 3.2.3](#) will be used. If all of the above are missing, then it is assumed the patient did not take BRV.

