## 8.2 Withdrawal criteria

Patients are free to withdraw from the NIS at any time, without prejudice to their continued care.

Physicians are free to add or withdraw any medication or to withdraw the patient from the study at their own discretion.

If the physician elects to permanently stop BRV treatment, the patient will be withdrawn from the study.

The primary reason for withdrawal from the NIS must be documented in the patient's eCRF. When the primary reason for withdrawal is lack of effectiveness or an AE, both must be reported as described in [Section 10.1.8](#) of the protocol.

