#### **4.2.2 Times and Dates**

Partial dates may be imputed for statistical analyses for specific outcomes according to the following rules. There will be no imputation of missing times. In general, imputed dates will not be shown in listings with the exception of showing imputed dates alongside partial dates for key derivations.

Imputation of partial first BRV administration date:

- If the day of first BRV administration is missing and the month and year are the same as the month and year of Visit 1 then the date of Visit 1 will be imputed as the date of first BRV administration. Otherwise impute 1st of the month.
- If the day and the month of first BRV administration are missing then no imputation of the partial date will be done.

Imputation of partial start dates:

- If only the month and year are specified and the month and year of first dose is not the same as the month and year of the start date, then use the 1st of the month.
- If only the month and year are specified and the month and year of first dose is the same as the month and year of the start date, then use the date of first BRV administration.
- If only the year is specified, and the year of first dose is not the same as the year of the start date, then use January 1st of the year of the start date.
- If only the year is specified, and the year of first dose is the same as the year of the start date, then use the date of first BRV administration.
- If the start date is completely unknown, then use the date and time of first BRV administration.

Imputation of partial end dates:

- If only the month and year are specified, then use the last day of the month.
- If only the year is specified, then use December 31st of that year.
- If the stop date is completely unknown, do not impute the stop date.

The imputation rules should not create an inconsistency in the data.

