### 8.1 Statistical analysis of the primary variable

#### 8.1.1 Retention at 12 months

Patients who remain in the study and are on BRV treatment 1 year after their start of BRV will be classed as having 12 months of treatment retention. More specifically, a patient will be categorized as having 12 months BRV retention if they do not meet either of the following criteria:

- Date of study termination < date of first BRV administration + 330 days
- Date of last administration of BRV while in the study < date of first BRV administration + 330 days

Otherwise, patients meeting either of the bulleted conditions above will be categorized as not having 12 months BRV retention. Date of last administration of BRV will be derived as described in [Section 3.2.4](#). 330 days is used to represent 1 year of treatment in accordance with the visit window instructions given to sites (i.e., that the 12 month visit should not be prior to 330 days). This is to prevent classing patients as not having BRV retention when in fact they completed the study within 30 days of the target 360 days.

The number and percentage of patients achieving 12 months retention will be presented on the FAS along with a 2-sided exact (Clopper-Pearson) 95% CI for the percentage.

A by-patient listing of patient retention data including dates of first and last BRV administration, date of study termination, time to discontinuation of BRV or study termination, visit window target dates, and retention at 3, 6 (as described in [Section 8.2.1](#)), and 12 months will be listed on the All Subjects Documented set.

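### When a partial last-BRV date leaves the retention threshold in doubt, the SAP always treats the threshold as reached; the resulting bias runs one way and is probably small

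*SAP*

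**What the plan says.** SAP 3.2.4 takes the last BRV date from the Study Termination pages and adds: "If the date is partial, then use the imputation of partial end dates rules". SAP 4.2.2 gives those rules. For a date that lacks only the day it says: "If only the month and year are specified, then use the last day of the month". For a date of which nothing but the year is known, the instruction reads: "If only the year is specified, then use December 31". The section closes with a general limit: "The imputation rules should not create an inconsistency in the data".

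A wholly missing last date is handled differently. It falls back to the last end date on the BRV Medication page and then to the first BRV date.

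SAP 8.1.1 classes a patient as not retained at 12 months on either of two criteria. The first is met when the patient left the study fewer than 330 days after starting BRV. The second concerns the drug itself: "Date of last administration of BRV while in the study < date of first BRV administration + 330 days". On how the two combine, the section is explicit that "patients meeting either of the bulleted conditions above will be categorized as not having 12 months BRV retention". SAP 8.2.1 repeats the structure with 90 and 180 days. Protocol 8.2 links stopping the drug to leaving the study: "If the physician elects to permanently stop BRV treatment, the patient will be withdrawn from the study".

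**The concern.** The end-date rule chooses the latest day that the recorded part of the date allows. That suits a concomitant medication, where one wants to keep anything possibly still in use. Here it feeds the primary variable, which asks whether BRV lasted at least 330 days. If the known month or year contains the threshold, the true last dose may lie on either side of it, yet the rule always places it on or after. A truly retained patient can never be lost by this, while a patient who stopped early can be gained.

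The two fallback rules also pull in opposite directions. A wholly missing date can end at the first BRV date, which gives non-retention, while a partial date gets its most favourable value.

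At stake are the 12-month retention rate and the 3- and 6-month rates. Exposure duration (SAP 10.1) and time to discontinuation due to adverse drug reactions (SAP 10.2) use the same date.

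**Working it through.** **Inputs.** The imputation rules are from SAP 3.2.4 and 4.2.2; the thresholds and the either-criterion rule from SAP 8.1.1 and 8.2.1; the FAS target of 385 and the half-width of 0.05 from SAP 2.4. The documents give neither the number of partial dates nor the lag from last dose to termination, so lags are assumed below.

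**The plan's own figure.** n = 1.96² × 0.50 × 0.50 / 0.05² = 384.1, so 385. The half-width at 385 is 0.0499. This reproduces, and it serves only as a yardstick.

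**Rule.** Let T = first BRV + threshold, L = imputed last BRV and S = study termination. The patient is retained if L ≥ T and S ≥ T.

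**Worked cases at Day 330:**

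| First BRV | Recorded last BRV | Termination | T | L | Result |
|---|---|---|---|---|---|
| 15 Jan 2017 | Dec 2017 (true 3 Dec) | 5 Dec 2017 | 11 Dec 2017 | 31 Dec 2017 | Not retained: S < T |
| 15 Jan 2017 | Dec 2017 (true 3 Dec) | 20 Dec 2017 | 11 Dec 2017 | 31 Dec 2017 | Retained, wrongly |
| 15 Jan 2017 | May 2017 | 20 May 2017 | 11 Dec 2017 | 31 May 2017 | Not retained: both criteria |
| 15 Mar 2017 | 2017 | 20 Sep 2017 | 8 Feb 2018 | 31 Dec 2017 | Not retained: both criteria |

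Only the second row goes wrong: termination is past the threshold, the true last dose is before it, and the recorded month reaches it. A year-only date in the year of first dose can pass only if BRV began by 4 February (5 February in a leap year).

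**Does capping L at termination help retention?** With the cap, the condition is min(L, S) ≥ T and S ≥ T. That holds exactly when L ≥ T and S ≥ T, which is the rule without the cap. The 3-, 6- and 12-month results are unchanged.

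**How often would the error occur?** Assumptions: first doses spread evenly over 2016 to 2018, and true stops spread evenly over days 0 to 329, so that nobody is truly retained. Share of partial dates wrongly counted as retained at 12 months:

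| Lag from last dose to termination | Month-only | Year-only |
|---|---|---|
| Termination criterion ignored | 4.4% | 54.5% |
| 0, 7, 14 or 30 days, equally likely | about 2.4% | about 3.7% |
| Spread over 0 to 90 days | not tabulated; at most 4.4% | about 12% |
| 0 days | 0% | 0% |

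**Effect on the rate.** One wrongly retained patient moves it by 1/385 = 0.26 points. Suppose 1% to 5% of the FAS had year-only dates and all were true early stoppers. The shift is then 1% × 3.7% = 0.04 to 5% × 3.7% = about 0.18 points for lags to 30 days, and 1% × 12% = 0.12 to 5% × 12% = 0.6 points for lags to 90 days. The planned half-width is 5 points.

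**The case against.** The strongest reply is that the plan already contains the damage. Either criterion alone gives non-retention, Protocol 8.2 withdraws patients whose physician permanently stops BRV, and SAP 3.2.2 expects dropouts' Visit 4 before Day 330. Stopping and leaving are thus linked, and a patient with a partial last-dose date and termination after Day 330 is most often a real completer, for whom the rule makes no error. This stands, and it is why the effect is probably small.

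A reader might infer that every partial date is resolved in favour of retention. The documents do not support that: three of the four worked cases end as not retained. A reader might also take the share of year-only dates that pass the 330-day test for true stops at days 90, 180 and 270 (34%, 59% and 84%), or a bias of 0.6 to 2.9 points for 1% to 5% of the FAS, as the size of the problem. The percentages ignore the termination criterion. The points assume that every affected patient with termination on or after Day 330 truly stopped early.

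Two defences go less far. The no-inconsistency sentence does not say how it is to be applied. The inconsistency it most plainly rules out is a last dose in the study dated after termination, and a date capped there still passes when termination is past the threshold. The Kaplan-Meier analysis in SAP 8.1.2 takes event status from the Dropout page or the post-study prescription answer and uses the earlier of last BRV and termination. It is therefore partly protected, but its timing still uses the imputed date and it does not test the binary primary variable.

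Short lags are not guaranteed either. Protocol 8.2 sets no time limit and does not mention patients who stop on their own, and about 6 months separate Visits 3 and 4, so a stop in that interval may surface only at Visit 4.

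**Conclusion.** The point holds in a limited form. Within the last-BRV criterion, every partial date that leaves the threshold open is resolved as reached, at Day 90, 180 and 330 alike. The error is confined to patients with termination on or after the threshold and a true last dose before it. It can only raise retention.

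The size cannot be derived from the documents, because no count of partial dates is given. The rates of about 2% to 4% (lags of 0 to 30 days) and about 12% (year-only, lags up to 90 days) apply to true early stoppers before Day 330 with partial dates, not to the FAS. They rest on evenly spread starts and stops and on the assumed lags. A small bias is the likely outcome. The change is worth making because the rule leans one way in the primary variable, no planned analysis isolates it, and the correction is cheap.

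**What to change.** In SAP 3.2.4, for use in 8.1.1 and 8.2.1: when a partial last-BRV date spans the threshold (its earliest possible day is before the threshold and its latest is on or after it), count the patient as meeting the last-BRV criterion only if a BRV dose is documented on or after the threshold, on the BRV Medication page or in a visit dose record, including Visit 4. Otherwise count as not retained. Report the present latest-date rule as a sensitivity analysis, with the number of partial dates by type.

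Separately, state that the imputed last-BRV date is capped at study termination for exposure duration (10.1) and time to discontinuation due to adverse drug reactions (10.2). The cap can change those results; it does not affect retention.

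Cost: SAP wording and one derivation, from dose records that Protocol Table 17–1 already schedules at every visit. The downside is that a truly retained patient with no documented dose past the threshold becomes not retained, so the rate may be slightly lower. Showing both rules side by side makes that visible.

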## **8.2 Statistical analysis of the secondary variables**

### **8.2.1 Retention at 3 and 6 months**

Similar to the primary endpoint, patients will be classed as having 3 months BRV retention if they do not meet either of the following criteria:

- Date of study termination < date of first BRV administration + 90 days
- Date of last administration of BRV while in the study < date of first BRV administration + 90 days

Otherwise, patients meeting either of the bulleted conditions above will be categorized as not having 3 months BRV retention. 90 days is selected because at least 3 months BRV retention is required, hence a patient who attends a month 3 visit early and terminates BRV prior to Day 90, would not be classed as having 3 months retention.

Patients will be classed as having 6 months BRV retention if they do not meet either of the following criteria:

- Date of study termination < date of first BRV administration + 180 days
- Date of last administration of BRV while in the study < date of first BRV administration + 180 days

Otherwise, patients meeting either of the bulleted conditions above will be categorized as not having 6 months BRV retention. 180 days is selected because at least 6 months BRV retention is required, hence a patient who attends a month 6 visit early and terminates BRV prior to Day 180 would not be classed as having 6 months retention.

BRV Retention at 3 and 6 months will be summarized using the methods described in [Section 8.1](#) for the FAS and the modified FAS. BRV Retention at 3 and 6 months will be listed as described in [Section 8.1.1](#).

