## **10 SAFETY ANALYSES**

### **10.1 Extent of exposure**

The duration of exposure of BRV (days) while in the study is calculated as:

Date of last administration of BRV while in the study – date of first BRV administration + 1.

For snapshot analyses, patients with missing date of last administration of BRV while in the study will be imputed using the date of data cut-off for the analysis. This assumes that patients still ongoing in the trial are still taking BRV.

All exposure analyses will be performed on the SS and the modified FAS.

Exposure will be summarized using descriptive statistics of the continuous variable duration of exposure (days). In addition, the following categories of duration of exposure (days) will show the number of patients with 1 day to <3 months BRV (1-<90 days), 3 months to <6 months BRV (90-<180 days), 6 months to <12 months BRV (180-<330 days), and ≥12 months BRV (≥330 days).

The number and percentage of patients receiving each daily BRV dose at Day 2, Day 7, Day 14, Day 21, Day 30, Day 60, Day 90, Day 120, Day 150, Day 180, Day 240 and Day 330 will be

summarized in the following BRV dose categories ( $\leq 10\text{mg}$ ,  $>10$  to  $<50\text{mg}$ ,  $\geq 50\text{mg}$  to  $<100\text{mg}$ ,  $\geq 100\text{mg}$  to  $<150\text{mg}$ ,  $\geq 150\text{mg}$  to  $\leq 200\text{mg}$  and  $>200\text{mg}$ ). In addition, the total number of patients receiving each Dose category at any time on the study will be presented. Day 1 will be equal to the first BRV administration date. Day 2 is considered as the starting dose due to some patients only receiving 1 dose (afternoon dose only) on Day 1.

Time to BRV maintenance dose will be summarized descriptively and will be defined as:

Date of first intake of the BRV dose the patient remained on for the longest time during the treatment period – Date of first BRV administration.

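### The SAP 3.2.4 fallback for a missing last-dose date can score a study completer as non-retained in the primary analysis, and 8.1.2 gives that patient two different censoring dates

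*SAP*

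**What the plan says.** SAP 3.2.4 takes the last BRV dose from the Study Termination page, Dropout or Completed Subject. The fallback is the same for both: "For patients who have completed or withdrawn from the study, if the date of last administration is missing, then the last end date" on the BRV Medication page is taken. Then: "If that date is also missing then the date of first BRV administration". SAP 4.2.2 adds: "If the stop date is completely unknown, do not impute the stop date". A dose record still open therefore supplies no end date.

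SAP 8.1.1 uses the date derived in 3.2.4. A patient is non-retained at 12 months if study termination falls before first BRV plus 330 days, or if "Date of last administration of BRV while in the study < date of first BRV administration + 330 days". Meeting either condition is enough. SAP 8.2.1 has the same structure at 90 and 180 days, for example "Date of last administration of BRV while in the study < date of first BRV administration + 90 days". SAP 10.1 computes exposure as last dose minus first dose plus 1.

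SAP 8.1.2 defines the Kaplan-Meier event without the last-dose date: a Dropout page, or the answer No on whether BRV will be prescribed after exit. Its time variable is the earlier of last dose and termination, minus first dose, plus 1. A separate sentence censors everyone without an event at study termination.

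Two other passages bear on what a completer's missing date means. Protocol 8.2: "If the physician elects to permanently stop BRV treatment, the patient will be withdrawn from the study". For ongoing patients at a snapshot, SAP 3.2.4 says "For these patients the date of last administration of BRV will be imputed using the date of the data cut off", and SAP 10.1 explains: "This assumes that patients still ongoing in the trial are still taking BRV".

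**The concern.** A completer has by definition reached the end of the Observation Period. If that patient's last-dose field is blank, the fallback searches for an end date. Where the current dose record is open, the end date found belongs to an earlier dose step. Where there is no end date or no record, the last dose becomes the first dose. Either way the patient can fail the primary endpoint because of a date rule and not because BRV was stopped.

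The fallback can only move 12-month retention down. It can also lower 3- and 6-month retention and exposure. The patient stays in the FAS, because SAP 3.5 accepts a first-dose date alone as evidence of dosing. The Kaplan-Meier analysis, meant as a sensitivity analysis of the primary variable, can then disagree with it about the same patient, and the SAP leaves open on which day that patient is censored.

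**Working it through.** **Planning figure.** Inputs from Protocol 12.4 and SAP 2.4: two-sided 95%, expected proportion 0.50, half-width 0.05. n = 1.96² × 0.25 / 0.05² = 384.15 with the unrounded normal quantile, so 385 as stated. The half-width at 385 is 0.0499. This is the yardstick for the figures below.

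**One patient through the rules.** Assumed: first dose Day 1; one closed BRV record ending Day 60; current record open; Completed Subject page with termination on Day 361; last-dose date missing; post-exit answer Yes.

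- 3.2.4: last dose = Day 60, which is 59 days after first dose.
- 8.1.1: termination is 360 days after first dose and passes; 59 < 330 fails. Non-retained at 12 months.
- 8.2.1: 59 < 90 and 59 < 180. Non-retained at 3 and 6 months.
- 10.1: exposure 60 days.
- 8.1.2: no event. Censored on Day 361 by the sentence, on Day 60 by the formula.

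With no end date on record, the last dose is Day 1. The retention results are the same, exposure is 1 day, and the formula censors on Day 1.

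**Size per patient.** 1/385 = 0.26 points. For the enlarged study, 530 × 0.9 = 477 (assumed FAS), and 1/477 = 0.21 points. One point needs 4 of 385 (1.04) or 5 of 477 (1.05). Ten patients cost 2.6 or 2.1 points.

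With 385 patients and 192 true completers (Clopper-Pearson intervals, number affected assumed):

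| Completers affected | 12-month retention (95% CI) |
|---|---|
| 0 | 192/385 = 49.9% (44.8 to 55.0) |
| 10 | 182/385 = 47.3% (42.2 to 52.4) |
| 19 | 173/385 = 44.9% (39.9 to 50.1) |

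A shift close to the planned half-width needs about 10% of completers (19/192).

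**8.1.1 against 8.1.2.** Assumed: n = 477, 238 completers, 239 dropouts after Day 1 and by Day 330, k completers falling back to the first-dose date, none answering No. S(330) is the Kaplan-Meier estimate at Day 330.

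| k | 8.1.1 | S(330), censored at termination | S(330), censored on Day 1 |
|---|---|---|---|
| 5 | 233/477 = 48.8% | 238/477 = 49.9% | 1 − 239/472 = 49.4% |
| 10 | 228/477 = 47.8% | 238/477 = 49.9% | 1 − 239/467 = 48.8% |

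The two analyses differ under either reading of 8.1.2. If all k answered No, they become Day 1 events and S(330) = (238 − k)/477, equal to 8.1.1.

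**Late quantiles.** A retained completer has last dose and termination at least 330 days after first dose, so an exit answer of No can be an event only from Kaplan-Meier Day 331. A median or quartile first reached after Day 330 therefore depends on the exit answer. S(330) does not, apart from the date problem above.

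**The case against.** **The fallback may never operate.** It acts only when a dedicated field on the termination page is blank. Protocol 13.1 and 13.2.2 describe remote review for missing data plus computerized and manual checks, and the 8.1.1 listing shows first dose, last dose and termination dates together. No missing-date rate is given, and an open final record is an assumption about a CRF we cannot see. All of this stands. A reader might infer that the primary estimate is materially too low; the documents do not support that.

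**Protocol 8.2 does not prove continued treatment.** It covers a physician's decision to stop permanently. The SAP collects a last-dose date for completers and tests it separately from termination, so it does not equate the two. It is tempting to say that a Completed Subject page establishes BRV up to exit; it only makes that the expected case. Likewise, the snapshot rule concerns dates not yet due. The contrast with 3.2.4 is awkward, since completing with the date still missing moves the last dose backward, but it is not a formal contradiction.

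**4.2.2 closes by warning that imputation should not create inconsistent data.** A completer with a last dose on Day 1 looks like such a case. But that sentence governs the partial-date rules and does not replace the explicit sequence in 3.2.4.

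**Counting undocumented continuation as failure is conservative.** That is a legitimate choice for a bound. As the main rule it can assign Day 1 as the last dose of someone who finished the year, and the SAP does not present it as a deliberate conservative choice.

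**On 8.1.2,** a reader might take it as settled that the Kaplan-Meier analysis censors this patient at termination. The sentence says so; the formula does not. A reader might also conclude that the curve should stop at Day 330 or that exit answers should not be events. The exit rule was added deliberately in SAP Amendment 3, and 8.1.2 already gives numbers at risk and monthly estimates, so neither change follows.

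**Conclusion.** The point holds on the text. For a Completed Subject with a missing termination-page last-dose date and no late end date on record, 3.2.4 and 8.1.1 together give non-retention. The first-dose fallback carries this to 3 and 6 months and to 1 day of exposure. In 8.1.2 the same patient is not an event unless the exit answer was No, and the censoring date is stated inconsistently.

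The direction is certain: 12-month retention can only fall. The size is 0.26 points per patient at 385 or 0.21 at an assumed 477. The number of such patients is unknown and may be zero after cleaning, so this is a rule to correct before lock and not evidence of a biased result. An effect on seizure freedom follows only if Table 8-1 reads discontinuation of BRV from the same derived date, which the SAP does not say. In that case a seizure-free completer would become No under the first method or missing under the second.

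**What to change.** - **3.2.4.** For any Completed Subject with a missing last-dose date and no closed final BRV Medication record (record open, no end date, or no record at all), use the study termination date.
- **Same date throughout.** Apply it in 8.1.1, 8.2.1, 8.1.2 and 10.1, and in Table 8-1 if that table uses it.
- **Disclosure.** Report how many patients were imputed. Show 12-month retention with them counted as non-retained, as a bound; the two figures differ by the number imputed divided by the FAS size.
- **8.1.2.** Use one date, the earlier of derived last BRV and study termination, for both event and censoring times. Name S(330) as the estimate to compare with the 8.1.1 percentage. Keep the exit-event rule and the full curve, with a note that a median or quartile first reached after Day 330 depends on the exit answer.

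The cost is SAP wording, minor reprogramming and one extra table row; no new data are needed. The downside is that the termination date is the favourable assumption, which the bound discloses. One difference remains: a completer with a recorded last dose or termination before 330 days is non-retained in 8.1.1 but, unless the exit answer was No, not an event in 8.1.2. The 8.1.1 listing can identify such patients when the two figures are compared.
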